3.2 Study Design

This study is designed as a prospective, multicenter, single-blinded, randomized comparison IDE study between CellFX System and Cryosurgery. The Principal Investigator will select a sub-investigator to be the blinded investigator to classify the healing characteristics and wart clearance and/or reduction assessment of each subject's selected warts at baseline, post treatment and at 7-days, 30-days, 60-days, and 90-days following the last CellFX treatment or Cryosurgical procedure. This sub investigator will be blinded to the treatment assignment. The subject may not be blinded to the treatment assignment. The Principal Investigator can choose to be the blinded investigator and select a sub investigator to be the treating investigator.

Eligible subjects with a minimum of 2 and up to 8 warts meeting the inclusion and exclusion criteria will be enrolled. If the subject has more than 8 warts, the subject is excluded from the study. Warts may be present anywhere on the face except the scalp, nose and within the orbital region of the face. Plantar warts are also excluded. Subjects will be randomized to receive either a CellFX treatment or Cryosurgery. Selected warts for each treatment modality must be clearly separated in distance from each other so that wart treatment and side effects can be assessed by the blinded site investigator.

All eligible warts will receive at least one CellFX or Cryosurgical treatment. Each subject will be evaluated by the blinded site investigator at 7-days, 30-days, 60-days, and 90-days post-initial CellFX and Cryosurgical treatments. At the 30-day or 60-day follow-up visit, if any wart is classified as “not resolved”, the wart must receive an additional treatment. In case of a second or third retreatment, the subject will be evaluated by the blinded site investigator at 30-days, 60-days, and 90-days post-retreatment. Photography of the warts will be captured along with the blinded site investigator assessments at all visits.

Numbness (diminished/ altered sensation) Assessment: The treating investigator will conduct a “light touch” exam to all treated areas at baseline, 7 days and 30 days post initial treatment and 30 days post retreatment(s). Light touch is tested with a cotton wisp, feather, and/or even light finger touch. The subject will be asked how one area feels compared to another.

Note 1:

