Eligible warts that should be treated and do not receive a retreatment will be considered a protocol deviation. The reason(s) for not receiving an additional treatment will be collected on the electronic case report form (eCRF). These subjects will remain in the study and will be included in the ITT population.

Additionally, subjects can only receive two additional treatments or up to a maximum of three CellFX or Cryosurgical procedures.

Non-Treated Wart Criteria: Data will be collected on ineligible or non-treated warts for all enrolled subjects. Non-treated warts are defined as flat, periungual, subungual, mosaic, plantar, filiform and/or common warts that are excluded due to anatomic location. Photography of the non-treated warts will be captured at baseline and the last study visit.

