3.8 Clinical Study Duration

It is anticipated that the enrollment of subjects in this study will take approximately 3-4 months in duration. All subjects who only receive one treatment will return for follow-up visits at 7-days, 30 days, 60-days, and 90-days or up to a total of 5 study visits. For subjects who receive additional CellFX or Cryosurgery retreatments, at the 30-day or 60-day follow up visit, will return for additional follow-up for 90-days post last treatment or up to a total of 6 or 7 study visits. The total study duration will be approximately 9 months.

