- Photographic images of all treated warts will be taken with pre- and post-wart markings
- All warts will be clinically assessed by the blinded site investigator (wart healing characteristics, wart clearance and wart reduction assessments)
- Assessment of numbness in the treated area will be performed by the treating investigator

- If any wart is classified as “not resolved”, a second treatment with CellFX or Cryosurgery will be performed to the previously treated wart(s)

In case of a second CellFX or Cryosurgical treatment is required:

- Local anesthesia/numbing will be applied to each wart designated for a CellFX retreatment
- Each wart designated for a CellFX retreatment will be treated using pre-determined energy settings
- Each wart designated for Cryosurgical retreatment will be performed as outlined in protocol **Section 3.5**
- The subject will be asked to rate his/her pain immediately after each wart treated with CellFX and/or Cryosurgery by using a numerical rating score
- The subjects will be asked whether they felt muscle twitching immediately after each lesion treated with CellFX
- Immediately post-procedure, a wart healing characteristics assessment will be performed by the blinded site investigator
- Photographic images of all retreated warts will be taken post-treatment
- A light bandage and/or any physician recommended dressing may be applied before the subject leaves the clinic
- Any adverse events will be identified and documented with a live assessment by the blinded site investigator

4.8 60-Day Follow-up Visit (CellFX/Cryosurgical Treatment #3, if required)

- Photographic images all treated warts will be taken with pre- and post-wart markings
- All warts will be clinically assessed by the blinded site investigator (wart healing characteristics, wart clearances and wart reduction assessments)
- Assessment of numbness in the treated area will be performed by the treating investigator (only for those subjects who received a retreatment at the 30-day follow-up visit)

- If any wart is classified as “not resolved”, a third treatment with CellFX or Cryosurgery will be performed to the previously treated wart(s)

In case of a third CellFX or Cryosurgical treatment is required:

- Local anesthesia/numbing will be applied to each wart designated for a CellFX retreatment
- Each wart designated for a CellFX retreatment will be treated using pre-determined energy settings

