- Each wart designated for Cryosurgical retreatment will be performed as outlined in protocol **Section 3.5**
- The subject will be asked to rate his/her pain immediately after each wart treated with CellFX and/or Cryosurgery by using a numerical rating score
- The subjects will be asked whether they felt muscle twitching immediately after each lesion treated with CellFX
- Immediately post-procedure, a wart healing characteristics assessment will be performed by the blinded site investigator
- Photographic images of all retreated warts will be taken post-treatment
- A light bandage and/or any physician recommended dressing may be applied before the subject leaves the clinic
- Any adverse events will be identified and documented with a live assessment by the blinded site investigator

4.9 90-Day Follow-up Visit

- **This is the Final Study visit for any subject for whom all wart(s) were only treated one time**
- Photographic images of all treated warts will be taken with pre and post wart markings
- All treated warts will be classified as “resolved” or “not resolved” by the blinded site investigator
- Wart healing characteristics and wart reduction assessment will be performed by the blinded site investigator
- Assessment of numbness in the treated area will be performed by the treating investigator (only for those subjects who received a retreatment at the 60-day follow-up visit)
- 6-point subject satisfaction scale (for those subjects exiting the study)
- Photographic images will be collected on all non-treated warts (for those subjects exiting the study)
- Any adverse events will be identified and documented with a live assessment by the blinded site investigator

4.10 120-Day Follow-up Visit

- **This is Final Study visit for any subject who have undergone only 2 treatments and/or the last treatment performed at the 30-day follow-up**
- Photographic images of all treated warts will be taken with pre and post wart markings
- All treated warts will be classified as “resolved” or “not resolved” by the blinded site investigator
- Wart healing characteristics and wart reduction assessment will be performed by the blinded site investigator

- 6-point subject satisfaction scale (for those subjects exiting the study)
- Photographic images will be collected on all non-treated warts (for those subjects exiting the study)
- Any adverse events will be identified and documented with a live assessment by the blinded site investigator

4.11 150-Day Follow-up Visit

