- **This is Final Study visit for any subject for whom wart(s) were retreated at the 60-day follow-up**
- Photographic images of all treated warts will be taken with pre and post wart markings
- All treated warts will be classified as “resolved” or “not resolved” by the blinded site investigator
- Wart healing characteristics and wart reduction assessment will be performed by the blinded site investigator
- 6-point subject satisfaction scale
- Photographic images will be collected on all non-treated warts
- Any adverse events will be identified and documented with a live assessment by the blinded site investigator

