10.3.2.1 Stopping Rules

- a) Full dermal thickness ulcer in any subject, of any duration;
- b) Any depth ulcer or erosion lasting ≥ 30 days, in more than 2 of the first 20 subjects treated with CellFX or more than 10% of subjects treated after the first 20 subjects; and
- c) Scab or crust that is so severe at the 30 day visit that it would preclude additional treatment that day, in more than 2 of the first 20 subjects treated with CellFX or more than 10% of subjects treated after the first 20 subjects.

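### Section 4.10 lets a subject whose only retreatment was at Day 60 exit at Day 120, against Section 4.11, so warts treated at Day 60 can miss the 90-day skin-change reading

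*Combined protocol and SAP*

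**What the plan says.** Three visits can be the last one. Section 4.9 makes Day 90 final when every wart was treated once. Section 4.10 says of Day 120: "This is Final Study visit for any subject who have undergone only 2 treatments and/or the last treatment performed at the 30-day follow-up". Section 4.11 says of Day 150: "This is Final Study visit for any subject for whom wart(s) were retreated at the 60-day follow-up", with no condition on how many treatments the subject has had.

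Elsewhere the protocol ties follow-up to the last treatment. Section 3.8 says that retreated subjects "will return for additional follow-up for 90-days post last treatment or up to a total of 6 or 7 study visits". Section 3.2 asks for assessments 30, 60 and 90 days after a retreatment. Section 10.0 collects adverse events for 90 days after the last procedure. The skin-change co-primary endpoint in 6.1.1 is read 90 days after the last treatment, wart by wart.

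On when retreatment can happen, Section 3.2 opens its rule with "At the 30-day or 60-day follow-up visit, if any wart is classified as" unresolved, so both visits are treatment opportunities. Its Note 1 adds: "Eligible warts that should be treated and do not receive a retreatment will be considered a protocol deviation". Such subjects stay in the study and in the ITT population.

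**The concern.** The and/or in 4.10 joins two conditions that are not the same. A last treatment at Day 30 puts Day 120 at 90 days, as intended. Having had two treatments does so only if the second was at Day 30. If it was at Day 60, 4.10 releases the subject at Day 120 and 4.11 keeps the subject to Day 150.

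At stake is a reading for one of three co-primary endpoints, all of which must succeed (6.1, 6.1.4), and it is a safety endpoint. The loss would not obviously be random: whether a wart is first retreated at Day 60 can depend on how it behaved after the first treatment. Section 6.6 ties the validity of the GEE model to data missing completely at random. It also expects gaps to come from missed visits that remove all of a subject's warts at once, which does not describe an exit that the protocol itself directs and that affects only some warts.

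**Working it through.** **Inputs.** Treatment days 0, 30 and 60 and final visits at Days 90, 120 and 150 (Table 2; Sections 4.7 to 4.11). Visit window ±10 days for Visits 3 to 7 (Table 2). Required follow-up of 90 days after the last treatment (3.2, 3.8, 6.1.1, 10.0).

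**Formula.** Follow-up = final visit day − day of last treatment. Shortest = (visit − 10) − (treatment + 10); longest = (visit + 10) − (treatment − 10). Day 0 has no window.

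**Intended paths, which reproduce the protocol's 90 days:**
- Day 0 to Day 90: 90 − 0 = 90 days (80 to 100).
- Day 30 to Day 120: 120 − 30 = 90 days (100 + 10 − 40 = 70, to 130 − 20 = 110).
- Day 60 to Day 150: 150 − 60 = 90 days (140 − 70 = 70, to 160 − 50 = 110).

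**Path under the two-treatments limb of 4.10:**
- Day 60 to Day 120: 120 − 60 = 60 days (110 − 70 = 40, to 130 − 50 = 80).
- Shortfall against the required follow-up: 90 − 60 = 30 days, which is also the adverse event collection lost.

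**Can the path occur?** Section 4.10 counts treatments by subject. For the second to fall at Day 60, no wart may have been retreated at Day 30. Two routes fit the text: all warts were resolved at Day 30 and at least one was unresolved at Day 60; or every retreatment needed at Day 30 was missed, which Note 1 treats as a deviation without removing the subject.

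**What is lost and what is kept, for such a subject exiting at Day 120:**
- Warts treated at Day 60: the 30-day reading (60 + 30 = Day 90) and the 60-day reading (60 + 60 = Day 120) are obtained; the 90-day reading (60 + 90 = Day 150) is not.
- Warts last treated at Day 0: the 90-day reading is obtained at Day 90.

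So the clearance and wound-healing co-primaries, both read at 30 days, are intact. Only the skin-change co-primary is touched, and only for warts treated at Day 60.

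**The case against.** The best defence is that the rest of the protocol settles the matter. Section 4.11 covers any subject retreated at Day 60, and 3.2, 3.8, 6.1.1 and 10.0 all run to 90 days after the last treatment. The visit headings point the same way: "4.8 60-Day Follow-up Visit (CellFX/Cryosurgical Treatment #3, if required" numbers the Day 60 treatment as the third, so in that vocabulary two treatments means last treated at Day 30. Section 4.7 also requires retreatment of any unresolved wart at Day 30, which makes the path rare. And 6.6 already plans a longitudinal model on the 30-, 60- and 90-day results and a tipping-point analysis at 90 days.

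Most of this stands, and it limits the size. It does not remove the conflict: a subject on this path satisfies two final-visit rules, and nothing says which prevails. The analyses in 6.6 would examine the missing readings, using the 30- and 60-day results that remain, but would not recover them.

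A reader might infer more than the protocol supports:
- That the subject has no 90-day reading at all. The endpoint is wart-specific, and warts treated once are read at Day 90.
- That an assumed share of affected subjects adds the same number of points to the planned 15% loss. The endpoint is at wart level, only some of a subject's warts are affected, and no frequency is given.
- That an affected wart can never be seen at an interval the intended path allows. The ranges 40 to 80 and 70 to 110 days overlap at 70 to 80.
- That the affected subjects are those whose wounds were too severe to retreat at Day 30. Stopping rule (c) in 10.3.2.1 does contemplate "Scab or crust that is so severe at the 30 day visit that it would preclude additional treatment that day", but it sets a threshold, gives no expected rate, and does not say that such subjects are then treated at Day 60.

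**Conclusion.** Section 4.10 is wrong as written, and the error is minor. For a subject whose only retreatment was at Day 60, it allows exit a nominal 30 days before the skin-change reading and the end of adverse event collection for the warts treated that day. This rests on two conditions: that such subjects occur, which 3.2 and its Note 1 permit, and that a site applies 4.10 rather than 4.11. A site that follows 4.11 loses nothing. The number of warts affected is unknown and probably small. Any loss may depend on the course of the wart, but the protocol does not show its direction or that it would differ between arms.

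**What to change.** Reconcile 4.10 with 4.11, 3.2 and 3.8 so that the final visit depends only on the date of the subject's last treatment and always provides the assessment 90 days after it. Deleting the two-treatments clause and its and/or from 4.10 would do this: Day 120 would then be final only when the last treatment was at Day 30, and Day 150 whenever any wart was treated at Day 60. Table 2 labels Visits 5, 6 and 7 all as a final visit; a footnote giving the same rule would help sites.

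The cost is a one-line protocol edit. It adds no visit beyond the Day 150 visit that 4.11 already requires, and it changes neither the endpoint nor the analysis.

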4.12 Subject Withdrawal

A study subject has the right to discontinue participation at any time without penalty or loss of benefits to which the subject is otherwise entitled. A withdrawn subject will be treated according to standard of medical care and will not be replaced.

5.0 BENEFITS AND RISKS

5.1 Benefits

There are no guaranteed benefits from participation in this study. Participation in the study offers another dermatological approach to accomplish the same clinical effect as the typical treatment devices currently used to treat patients with warts. The information learned from this study may contribute to the ultimate use of a safer and more effective device and the availability of the device to treat benign lesions as an alternative for use in future patients.

5.2 Risks

For detailed information on the risks of the devices used in the study procedure, including a complete list of warnings, precautions, and potential adverse events, please refer to the Instructions for Use (IFU) for the Pulse Bioscience CellFX® System.

5.3 Mitigation of Risks

As with any dermatological procedure, appropriate safety precautions will be followed. Risks observed or theoretical adverse events have been mitigated through the Instructions for Use, physician training, and patient selection in the study protocol.

All efforts will be made to minimize these risks by:

- Site Selection
- Patient Population that represents the demographics of the U.S. with a uniform

distribution of Fitzpatrick Skin Types I, II, III and IV

- Ensuring compliance to the protocol and IFU
- Study monitoring
- Safety processes-protocol adverse events reporting requirements

6.0 STATISTICAL CONSIDERATIONS

Further details of planned analyses can be found in the statistical analysis plan (SAP).

6.1 Co-primary Endpoints

Clinical acceptance of treatment with the CellFX System for common warts requires non-inferior clearance response (effectiveness), non-inferior healing processes and non-inferior rates of adverse skin changes (safety) versus cryosurgery. Because these features are critically important for treatment acceptability, this study is designed with 3 co-primary endpoints. The endpoints must demonstrate non-inferiority for the study to be considered successful.¹¹

All 3 co-primary endpoints are assessed with wart as the unit of analysis, but the analyses will be adjusted for within-subject correlation. The co-primary safety endpoints are the proportion of warts with adverse events related to wound healing (scabbing, swelling, crusting, blister, scar or ulcer) at 30 days after the last treatment and adverse skin changes (the presence of hyperpigmentation, hypopigmentation or scarring) at 90 days post last treatment. The co-primary effectiveness endpoint is the proportion of warts classified as “resolved” at 30 days post last treatment.

6.1.1 Co-primary Safety Endpoints

The wound healing safety endpoint is the presence or absence of a wound healing safety event at 30 days from the last CellFX or Cryosurgical treatment as assessed by the blinded site investigator. The wound healing safety event is defined as the presence of scabbing, swelling, crusting, blister, scar or ulcer. The timing of the evaluation of this endpoint is wart specific as some warts may not require multiple treatments with CellFX or Cryosurgery. Warts will be categorized as having a primary safety event if any component (scabbing, swelling, crusting, blister, scar or ulcer) is present at the follow-up visit 30 days after the last treatment.

The statistical hypotheses to be evaluated for the wound healing primary safety endpoint are:

$$H_0: p_{CellFX} - p_{Cryo} \geq 15\% \text{ at 30 days post last treatment, versus}$$

$$H_A: p_{CellFX} - p_{Cryo} < 15\% \text{ at 30 days post last treatment}$$

Where p_{CellFX} and p_{Cryo} are the proportion of warts with a composite wound healing safety event (scabbing, swelling, crusting, blister, scar or ulcer) in each treatment group. The null hypothesis will be rejected if the upper bound of the 2-sided 95% confidence interval for the difference in proportions ($p_{CellFX} - p_{Cryo}$) is less than 15%. This approach is equivalent to a 1-sided test with a 2.5% type I error rate.

The skin change safety endpoint is the presence or absence of a skin change safety event at 90 days from the last CellFX or Cryosurgical treatment as assessed by the blinded site investigator. The skin change safety event is defined as the presence of hyperpigmentation, hypopigmentation, or scarring. The timing of the evaluation of this endpoint is wart specific as some warts may not require multiple treatments with CellFX or Cryosurgery. Warts will be

categorized as having a skin change safety event if any component (hyperpigmentation, hypopigmentation, or scarring) is present at the follow-up visit 90 days after the last treatment.

The statistical hypotheses to be evaluated for the skin change primary safety endpoint are:

$H_0: p_{CellFX} - p_{Cryo} \geq 15\%$ at 90 days post last treatment, versus

$H_A: p_{CellFX} - p_{Cryo} < 15\%$ at 90 days post last treatment

Where p_{CellFX} and p_{Cryo} are the proportion of warts with a composite skin change safety event (hyperpigmentation, hypopigmentation, or scarring) in each treatment group. The null hypothesis will be rejected if the upper bound of the 2-sided 95% confidence interval for the difference in proportions ($p_{CellFX} - p_{Cryo}$) is less than 15%. This approach is equivalent to a 1-sided test with a 2.5% type I error rate.

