4.2 Subject Selection

4.2.1 Inclusion Criteria

Candidates for this study must meet **ALL** the following criteria:

1. Subject is at least 18 and no older than 80 years of age.
2. Subject has a Fitzpatrick Skin Type I, II, III or IV.
3. Subject gives voluntary, written informed consent to participate in this clinical investigation and from whom consent has been obtained.
4. Subject must comply with study procedures including all follow-up visits.
5. Subject is willing to have warts treated in a single treatment session and understands that their warts may undergo multiple treatment sessions at subsequent visits.
6. Subject must have a minimum of 2 warts and up to 8 warts to be treated.
7. Subject with a clinical diagnosis of common warts located on hands and fingers or other body areas that are not located on the scalp, nose, within the orbital region of the face, plantar, genital or periungual area.
8. For study purposes, the warts must be no greater than 3 mm in height and must not exceed 10 mm x 10 mm at their largest dimension.
9. Each wart must appear alone and discrete and not appear in clusters.
10. Each wart must have been present for at least 4 weeks.
11. Subject consents to have photographs taken of the warts.
12. Subject agrees to refrain from taking an antihistamine including those used for gastric symptoms(e.g., Loratadine, Desloratadine, Cetirizine, Fexofenadine, Levocetirizine, Azelastine, Ranitidine, Cimetidine, Famotidine, and Nizatidine) up to 48 hours before enrollment and each scheduled follow-up visit, to facilitate an adequate wash-out period.
13. Subject agrees to refrain from using all other wart removal products or treatments (e.g. topical medication including over-the-counter medications) during the study period.

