4.2.2 Exclusion Criteria

Candidates will be excluded from the study if **ANY** of the following apply:

1. Subject with more than 8 visible warts in total anywhere on the body.
2. Presence of genital or anal warts will exclude subject participation in study, including treatment of warts on other areas.
3. Periungual, subungual, mosaic, plantar, or filiform warts will not be treated in the study. However, presence of these wart types in addition to warts that meet inclusion criteria will not exclude a participant from the study.
4. Subject has an implantable electronic medical device.(i.e., pacemaker, implantable cardioverter defibrillator)
5. Subject has an active infection or history of infection in designated test area within 90 days prior to first treatment.
6. Subject is prone to Koebnerization or has any of the following conditions (e.g., psoriasis, vitiligo, lichen planus, or an autoimmune disorder of the skin)
7. Subject is not willing or able to sign the Informed Consent.

8. Subject is known to be immune compromised.
9. Subject has allergies to Lidocaine or Lidocaine-like products.
10. Subject is a member of a vulnerable population including pregnant women and individuals employed by the Sponsor, clinic site, or entity associated with the conduct of the study.
11. Have any condition or situation which, in the Investigator's opinion, puts the subject at significant risk, could confound the study results, or may interfere significantly with the subject's participation in the study.
12. Use of any other investigational drug, therapy, or device within the past 30 days of enrollment or concurrent participation in another research study.
13. Subject was previously treated with CellFX for warts.

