4.5.3 CellFX / Cryosurgical Procedures

- Up to 8 clinically diagnosed warts that meet study criteria will be selected by the treating investigator prior to assigning warts or taking baseline enrollment photos
- The treating investigator will conduct a numbness assessment on the selected warts that will be treated
- Photographic images will be collected on all non-treated warts
- The site will log onto the Captivate EDC system. The randomization will include the type of treatment (CellFX or Cryosurgery) that the subject will be assigned
- A template may be used to determine which CellFX treatment tip size will be used for each wart – sizes range between 1.5 mm x 1.5 mm and 10.0 mm x 10.0 mm. Each wart will be numerically labeled using the Canfield two dot system
- The blinded site investigator will perform the baseline/enrollment wart(s) assessment (wart healing characteristics)
- Photographic images of each wart will be taken prior to using local anesthesia/numbing
- Local anesthesia/numbing will only be applied to warts treated with CellFX
- Each subject randomized to CellFX will be treated with pre-determined energy settings; each subject randomized to Cryosurgery will be treated as defined in **Section 3.5**
- The subject will be asked to rate his/her pain immediately after each wart treated with the CellFX and Cryosurgical procedure by using a numerical rating score
- The subjects will be asked whether they felt muscle twitching immediately after each lesion treated with CellFX
- Immediately post-procedure, a wart healing characteristics assessment will be performed by the blinded site investigator
- Photographic images of all treated warts will be taken post-treatment
- A light bandage and/or any physician recommended dressing may be applied before the subject leaves the clinic
- Any adverse events will be identified and documented with a live assessment by the blinded site Investigator

4.6. 7-Day Follow-up Visit

- Photographic images of treated warts will be taken with pre- and post- wart markings
- The blinded site investigator will perform wart(s) assessments (wart healing characteristics and wart reduction)

- Assessment of numbness in the treated area will be performed by the treating investigator
- Any adverse events will be identified and documented with a live assessment by the blinded site investigator

4.7 30-Day Follow-up Visit (CellFX/Cryosurgical Treatment #2, if required)

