6.5 Sub-Group Analyses

Primary and secondary endpoints will be evaluated for the ITT and PP populations, as well as analyzed in strata based on the following sub-groups:

- Number of treated warts (2 to 4 or 5-8)
- Age
- Prior treatment for treated warts
- Gender
- Clinical Site
- Treatment Energy Level
- Size of CellFX Treatment Tip
- Total Energy Density
- Number of Treatments

These analyses are meant to assess consistency of treatment effects only, and this study is not powered for inference within subgroups.

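### Both safety co-primaries count signs present at follow-up without reference to the wart's own baseline, so pre-existing scars and pigment change can score as events and shrink the arm difference, whichever arm is worse

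*Combined protocol and SAP*

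**What the plan says.** **Event rules (protocol 6.1.1).** The skin-change composite rests on presence alone: "The skin change safety event is defined as the presence of hyperpigmentation, hypopigmentation, or scarring". A wart has a skin-change event "if any component (hyperpigmentation, hypopigmentation, or scarring) is present at the follow-up visit 90 days after the last treatment". It has a wound-healing event "if any component (scabbing, swelling, crusting, blister, scar or ulcer) is present at the follow-up visit 30 days after the last treatment". Neither rule refers to the wart's state before treatment. Section 6.1 describes the first composite as "the proportion of warts with adverse events related to wound healing", a label that suggests something caused after enrolment, but the operative rule is presence.

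**Baseline rating (4.5.3 and Table 2).** At Visit 1, "The blinded site investigator will perform the baseline/enrollment wart(s) assessment (wart healing characteristics"). Section 6.1.1 does not use this rating. By contrast, the secondary endpoint on wart size (6.2, item 5) is a change from baseline with baseline size in the model.

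**Entry of previously treated warts.**
- Inclusion 13: "Subject agrees to refrain from using all other wart removal products or treatments", but only for the study period.
- Exclusion 12 sets a pre-enrolment window, limited to investigational products: "Use of any other investigational drug, therapy, or device within the past 30 days of enrollment".
- Exclusion 13 bars earlier CellFX treatment of warts. Nothing bars earlier freezing, acids or laser.
- Section 6.5 expects such warts, since it lists the subgroup "Prior treatment for treated warts".
- Section 3.3 stratifies randomisation by wart count only.

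**The concern.** The documents themselves say that earlier wart therapies leave marks of the kind the skin-change composite counts. Section 1.3 reports hyper- and hypopigmentation after chemical agents and dark spots after cryotherapy. Section 6.3 uses 29% hypopigmentation for cryosurgery.

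A wart that enters with such a mark, and still has it at the endpoint visit, is an event in either arm whatever the study treatment did. Randomisation balances these warts on average, so they do not favour an arm directly. They add the same amount to both rates and leave fewer warts in which the treatments can differ. The risk difference shrinks toward zero. In a non-inferiority test, that makes a truly unacceptable excess easier to miss and a true advantage harder to show. Two of the three co-primaries share the rule, and the study succeeds only if all three pass.

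**Working it through.** **Inputs.** Margin 15 points and one-sided alpha 2.5% (6.1.1). Skin-change rates 32.5% for CellFX and 40% for cryosurgery, within-subject correlation 0.55, 3 warts per subject, at least 88% power, and 63 subjects (189 warts) per arm (all 6.3). The share b is not in the documents. It is an assumption, taken here from 0 to 20%, equal in both arms and independent of new events.

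**1. The plan's own figure.** With unpooled variance, unadjusted warts per arm = (1.960 + 1.175)² × (0.40 × 0.60 + 0.325 × 0.675) / (0.15 + 0.075)² = 9.828 × 0.4594 / 0.0506 = 89.2, so 90. The design effect is 1 + (3 − 1) × 0.55 = 2.1, and 90 × 2.1 = 189 warts = 63 subjects, which matches. (Section 6.3 gives 97 warts before adjustment, against 90 here; the steps below use only the 189.)

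**2. Effect of carry-over on the difference.** Observed rate = b + (1 − b)p. So observed difference = [b + (1 − b)p₁] − [b + (1 − b)p₂] = (1 − b)(p₁ − p₂). A 15-point margin on the observed scale therefore tolerates 15/(1 − b) points of new events.

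**3. Standard error.** Let c and t be the observed cryosurgery and CellFX rates. Then SE = √{[c(1 − c) + t(1 − t)] × 2.1/189}.

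**4. Type I error at a true excess of +15 points** (40% against 55% new events) = Φ[(0.15 − 0.15(1 − b))/SE − 1.96]. At b = 20%: c = 0.52, t = 0.64, SE = 0.0730, and Φ(0.030/0.0730 − 1.96) = Φ(−1.549) = 6.1%.

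**5. Power if the planning rates are new-event rates** = Φ[(0.15 + 0.075(1 − b))/SE − 1.96]. At b = 20%: c = 0.52, t = 0.46, SE = 0.0744, and Φ(0.210/0.0744 − 1.96) = Φ(0.863) = 80.6%.

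| b (assumed) | True excess tolerated | Type I error, skin change | Power, skin change |
|---|---|---|---|
| 0 | 15.0 points | 2.5% | 88.3% |
| 5% | 15.8 | 3.2% | 86.1% |
| 10% | 16.7 | 4.0% | 84.1% |
| 20% | 18.8 | 6.1% | 80.6% |

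A clustered simulation (63 subjects with 3 warts per arm, 20,000 runs) gave type I errors of 2.5%, 3.1%, 3.9% and 5.9%, in agreement. The wound-healing composite gives the same type I errors to one decimal at equal b (3.2%, 4.0%, 6.1%), but its b should be smaller because mainly its scar component can carry over.

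**6. The alternative reading of the planning rates.** If they already include pre-existing marks, the planned power stands and the new-event rates are lower. At b = 10% they would be (0.40 − 0.10)/0.90 = 33.3% and (0.325 − 0.10)/0.90 = 25.0%.

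**The case against.** **Direction.** A reader might infer that the definition pushes the trial toward a non-inferiority finding in general. The documents do not support that. Section 6.3 plans on fewer events with CellFX for both composites (32.5% against 40%, and 37.6% against 43%). In that case dilution removes part of its advantage and works against success. The anti-conservative case arises only if CellFX is truly worse, though that is the case the test exists to guard against.

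**Size.** A reader might multiply the 52% of recalcitrant warts in the feasibility study (1.5) by the 40% cryosurgery rate (6.3) and infer that b is about 21%. This does not hold:
- Recalcitrant is not defined as previously treated.
- That cohort had 19 subjects and 31% plantar warts, which are excluded here.
- The 40% is a planning rate for one therapy, 11 points of it assumed.
- A mark matters only if it lasts to 90 days after the last study treatment, which is 90 to 150 days after the first. Section 1.5 calls the hyperpigmentation seen in the pivotal study transient.

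**Acute signs.** Scabs, crusts, swelling and blisters are unlikely to persist from Visit 1. Section 1.3 gives 7 to 14 days for healing after cryotherapy. This stands, and limits the point mainly to pigment change and scarring.

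**Clearance.** A reader might infer a similar effect on effectiveness, from late response to recent earlier treatment. The documents give nothing to size it, and it is not part of this point.

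**Already handled.** Section 6.1 uses adverse-event language, 6.5 has a prior-treatment subgroup, and 6.0 defers detail to the SAP. The label does not alter the explicit rule in 6.1.1, and 6.5 itself says that subgroups are not powered for inference. The supplied text shows no baseline adjustment. One may exist in the SAP or the case report forms, and 6.1.1 would then need to agree with it.

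**Conclusion.** The gap in the definition is real: as written, 6.1.1 counts a scar or pigment change that was on the wart before treatment, although a blinded baseline rating is collected. Its consequence is conditional and of unknown size. For b between 5% and 20%, one-sided type I error at a true 15-point excess is about 3.2% to 6.1%. Under the planned CellFX advantage, skin-change power is instead about 86% to 81%. At b of 5% or less the effect is small.

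These figures assume that marks are balanced by arm, independent of new events and persistent to the endpoint visit. The power figures also assume that the planning rates are new-event rates. Because the correction uses data already scheduled, it is worth making despite the uncertainty about b.

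**What to change.** 1. In 6.1.1, count a component as an event only if it is new or worsened relative to the blinded rating of the same wart at Visit 1. Specify the pre-treatment rating, because 4.5.3 has a second one immediately after the procedure. Requiring only that the component was absent at baseline is not enough: a marked wart could then never score that component, the difference for it would still be multiplied by (1 − b), and worsening would be hidden.
2. Keep the presence-based version as a sensitivity analysis, and add one restricted to warts unmarked at baseline.
3. Report the baseline prevalence of each component, and prior treatment, by arm. This shows what b could be.
4. Confirm that the Visit 1 form captures pigment change and scarring for each wart, with enough grading to judge worsening.

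Cost: endpoint wording, two sensitivity analyses and a check of the form, with no new visits. Event rates may come out somewhat lower than the planning rates in 6.3, so those should be revisited. No washout length is proposed. Marks that affect the skin-change endpoint must last 90 to 150 days from first treatment, so a short interval such as the 30 days in Exclusion 12 would not remove them.
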